2. PROTOCOL SYNOPSIS AND RESEARCH SUMMARY

2.1 Purpose

Given that many patients with HCC are not surgical candidates (for either resection or transplant), PLA techniques have become the standard non-operative approach. Non-randomized data have shown that the local control of HIGRT is comparable to that of PLA. Direct comparison of these two modalities via a randomized controlled clinical trial is the next logical step.

This research protocol will directly compare Percutaneous Local Ablation (PLA) to Hypofractionated Image-Guided Radiation Therapy (HIGRT) for patients with Hepatocellular Carcinoma (HCC) who are not surgical candidates or decline surgery while undergoing care at the Durham VA or at Duke Cancer Center.

Primary Objective

To compare change in Quality of Life (QOL), as defined by the European Organization for Research and Treatment of Cancer Quality of Life Questionnaire Core-30 (EORTC C-30), from baseline to 1 month post treatment in patients receiving PLA vs HIGRT.

Secondary Objectives

1. To estimate the difference in change in QOL in patients receiving PLA vs HIGRT, as measured EORTC C-30, from baseline to 3 months post-treatment
2. To estimate the difference in change in QOL in patients receiving PLA vs HIGRT, as measured EORTC C-30, from baseline to 6 months post-treatment
3. To estimate the difference in change in QOL in patients receiving PLA vs HIGRT, as measured by FACT-Hep, from baseline to 1 month, baseline to 3 months and baseline to 6 months post-treatment
4. To assess for grade ≥ 2 acute toxicity within 90 days of treatment initiation
5. To estimate the total healthcare system cost associated with PLA vs HIGRT from time of intervention through 90 days post treatment

Exploratory Objectives

1. To assess for grade 3+ late toxicity (>90 days post ablative therapy or radiation therapy)
2. To evaluate local control at the treated site within the liver
3. To evaluate distant liver recurrence (intrahepatic lesions other than treated lesion)
4. To evaluate median progression free survival (PFS)
5. To evaluate median overall survival (OS)

Hypotheses

For the primary endpoint of change in QOL at 1 month post treatment versus baseline, HIGRT will have significantly better patient reported global QOL than PLA.

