Ninety patients will be randomized with equal allocation to the two arms. Randomization will be stratified by whether the baseline global QOL score is < 60 or ≥ 60 , where QOL is measured by the EORTC QLQ-C30 scale. We anticipate that approximately 10% of the accrued patients will withdraw before 1 month, leaving 80 evaluable patients to be used in the statistical analyses. The general linear model will be used to test for an arm effect (in patients receiving PLA vs HIGRT) by regressing change across time in QOL on arm, controlling for the baseline value of QOL, Child Pugh score, and time between baseline and end of treatment. To calculate the power of the arm effect (in patients receiving PLA vs HIGRT) on change in QOL, we first note that the standard deviation of a normally distributed change score (SD_C) depends upon the SD of the pre-score, the SD of the post-score, and the Pearson correlation (ρ) between the two scores. If the SD's of the pre-score and the post-score are assumed equal and the correlation between them is 0.50, then $SD_C = SD$. For purposes of the power calculation we assume that $SD=10$ and $\rho = 0.5$; therefore $SD_C = 10$. Assuming 40 evaluable patients per arm, the two-sample t-test (1-sided alpha = 0.10) of an arm difference in change across time in QOL has power 0.82 when the true arm difference in change score is 5 (i.e., 50% of SD_C). An arm difference of 50% of a standard deviation of an outcome variable is generally considered to be a "medium"-sized effect. In order to have 40 evaluable patients per treatment arm, 90 patients will be accrued (assuming drop out prior to the 1 month EORTC QOL-C30 questionnaire).

After randomization, patients may decline the randomized treatment but will continue to be evaluable for all study outcomes if treated with MWA or HIGRT. All endpoints will be analyzed per randomized arm and per treatment delivered. If the patient does not receive either SBRT or MWA, the patient will be withdrawn from the study.

Secondary Endpoints:

[figure not shown]

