1. *To estimate the change in QOL in patients receiving PLA vs HIGRT, as measured by EORTC C-30, from baseline to 3 months post-treatment.* The mean difference between arms in change from baseline to 3 months in QLC-C30 will be estimated with their 95% confidence intervals [CI]. To calculate these CI's, the mean arm difference in QOL and its standard error will be estimated from a general linear model in which change in QOL is regressed on arm, controlling for the baseline value of QOL and the Child Pugh score.
2. *To estimate the change in QOL in patients receiving PLA vs HIGRT, as measured by EORTC C-30, from baseline to 6 months post-treatment.* The mean difference between arms in change from baseline to 6 months in QLC-C30 will be estimated with their 95% confidence intervals [CI]. To calculate these CI's, the mean arm difference in QOL and its standard error will be estimated from a general linear model in which change in QOL is regressed on arm, controlling for the baseline value of QOL and the Child Pugh score.

3. *To estimate the change in QOL as measured by FACT-Hep in patients receiving PLA vs HIGRT.* Change in FACT-Hep score from baseline to 1 month, baseline to 3 months and baseline to 6 months will be calculated for each patient, and the mean arm difference in change will be estimated with its 95% CI. The CI will be estimated as described for Secondary Objective 1.
4. *To estimate grade ≥ 2 acute toxicity within 90 days of treatment initiation.* CTCAE version 4 will be used for all toxicity assessments. The acute toxicity rate will be defined as any grade 2+ toxicity occurring during treatment through 90 days post-PLA or post-HIGRT. The acute toxicity rate with its exact 95% confidence interval will be estimated within each arm. The arm difference in acute toxicity rate will be estimated with its 95% CI. We will also estimate the rate of hospitalization due to treatment complications with its 95% CI and the proportion of patients requiring treatment breaks longer than 7 days from HIGRT, with its 95% CI.

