7.1.3 Safety Considerations

An **interim analysis** will be performed after the first 40 patients have been followed for 90 days after completion of study therapy. Accrual will not be halted during this analysis. All treatment-related grade 4-5 AEs occurring within 90 days of treatment will be tabulated and reviewed. If > 20% of patients experience grade 4-5 AEs attributable to treatment, a decision will be made to either: 1) halt the trial and all further accrual, 2) amend the protocol for more aggressive dose modification and/or 3) institute additional clinical monitoring.

Anticipated risks associated with PLA include:

- pain (muscle aches or spasm may occur for 3-5 days)
- nausea/vomiting
- infection
- fever
- liver damage
- blood vessel/nerve damage; this could require admission to hospital

Rare but very serious PLA risks include:

- liver damage which could cause liver failure
- bleeding from the liver which could be life threatening
- liver abscess (serious infection)

Anticipated risks associated with HIGRT include:

- fatigue
- pain
- nausea/vomiting

- **Rare but very serious HIGRT risks include:**
- liver damage which could cause liver failure
- rib fracture
- chest wall pain

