8.4 Localization, Simulation

All patients will undergo standard of care CT-based treatment planning in custom made immobilization devices. CT scan range must allow simultaneous view of the patient anatomy and fiducial system for stereotactic targeting (if used) and be adequate to ensure contouring of all targeted lesions, as well as necessary organs at risk (OAR). High-resolution CT scans should be obtained with uniform slice thickness of $\leq 3\text{mm}$ throughout.

The use of IV contrast is preferred. If there is a contraindication for IV contrast an abdominal MRI must be available for treatment planning. The use of other contrast agents is left to the discretion of the treating oncologist. If possible, the use of triphasic (arterial, portal venous, and delayed imaging) is recommended using a flow rate of 4-5ml/sec and 175ml of contrast.

Regions of high vascular contrast in the planning dataset are recommended to be converted to water equivalent density if used for planning (at the discretion of the treating physician). Planning datasets without intravenous contrast may be used for dose calculation.

Ideally a liver-specific MRI will be available and possibly fused with the treatment planning CT scan for target delineation.

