8.5 Respiratory Motion Assessment and Management

All respiratory motion should be evaluated by appropriate means including 4D CT scan, imaging of implanted fiducial marker, or fluoroscopy at the time of simulation.

Respiratory motion management (RMM) including abdominal compression, active breathing control, breath hold, end expiratory gating, or fiducial marker tracking, is recommended for any lesion to be treated with motion $> 5\text{mm}$. A recommended approach would be to use an ITV technique for motion $< 1\text{cm}$, but for motion $> 1\text{cm}$ (typically too large for a free breathing ITV) motion management including but not limited to abdominal compression, active-breathing control (ABC), gating, breath hold, etc. should be used.

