10.3 Treatment Period

Treatment period will be from start to finish of HIGRT or date of ablation based on randomization. Assessment will be performed by the study key personnel at baseline then months 1, 3 and 6 post-treatment for QOL surveys. They will also undergo weekly assessment by radiation oncologist during radiotherapy.

Restaging imaging and labs (LFTs, and AFP, INR) will be performed as per standard of care for HCC (typically 1 month post-treatment, 3 months post treatment and then every 3 months thereafter). Deviations from standard of care follow up for patients are at the discretion of the treating physicians.

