12.1 Adverse Events

An adverse event (AE) is any untoward medical occurrence in a subject receiving study therapy and which does not necessarily have a causal relationship with this treatment. For this protocol, the definition of AE also includes worsening of any pre-existing liver disease. An AE can therefore be any unfavorable and unintended or worsening sign (including an abnormal laboratory finding), symptom, or disease temporally associated with receiving either PLA or HIGRT. Abnormal laboratory findings without clinical significance (based on the PI's

judgment) should not be recorded as AEs. But laboratory value changes that require therapy or adjustment in prior therapy are considered adverse events.

From the time the subject signs the informed consent form through the End of Study visit (as defined in Section 11.4), all AEs must be recorded in the subject medical record and adverse events case report form.

AEs will be assessed according to the CTCAE version 4.0. If CTCAE grading does not exist for an AE, the severity of the AE will be graded as mild (1), moderate (2), severe (3), life-threatening (4), or fatal (5).

Attribution of AEs will be indicated as follows:

- Definite: The AE is clearly related to the study therapy
- Probably: The AE is likely related to the study therapy
- Possible: The AE may be related to the study therapy
- Unlikely: The AE is doubtfully related to the study therapy
- Unrelated: The AE is clearly NOT related to the study therapy

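### The acute-toxicity count starts with treatment, so harms of HIGRT's optional fiducial implantation that resolve earlier are missed, while PLA's same-session procedural harms are counted

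*Combined protocol and SAP*

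**What the plan says.** **The endpoint.** The secondary objective in Section 2.1 is "To assess for grade ≥ 2 acute toxicity within 90 days of treatment initiation". Secondary Endpoint 4 in Section 4 defines the rate as "any grade 2+ toxicity occurring during treatment through 90 days post-PLA or post-HIGRT". It is estimated within each arm, and the arm difference is given with a 95% confidence interval.

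**The treatment period.** Section 10.3: "Treatment period will be from start to finish of HIGRT or date of ablation based on randomization". No section names the event that starts HIGRT. Sections 3.1 and 8.1 describe HIGRT as the delivery of fractions. Section 1 uses the term for simulation, planning and delivery together.

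**Steps before HIGRT delivery.** Section 8.5 lists among the means of assessing motion "imaging of implanted fiducial marker, or fluoroscopy at the time of simulation", and it also allows tracking of fiducial markers. Section 8.4 prefers IV contrast at the planning scan and recommends a triphasic scan, where possible, "using a flow rate of 4-5ml/sec and 175ml of contrast". Fiducials are optional in Sections 8.4 and 8.9.

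**Steps in the PLA session.** Under Section 9.1, sedation or anaesthesia, antenna insertion and any contrast all take place on the day of ablation.

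**Recording and interim review.** Section 12.1 records all adverse events "From the time the subject signs the informed consent form through the End of Study visit". For the interim review, Section 7.1.3 says "All treatment-related grade 4-5 AEs occurring within 90 days of treatment will be tabulated and reviewed".

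**Untreated patients.** Section 4: "If the patient does not receive either SBRT or MWA, the patient will be withdrawn from the study". Section 10.7.2 says that subjects who withdraw early are still followed for primary and secondary endpoints by intention to treat. Section 10.7.3 allows replacement of those who withdraw before protocol therapy begins.

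**The concern.** A harms comparison is fair when each arm is charged with everything its treatment strategy requires. PLA is a single session, so its invasive and pharmacological steps share a date with the treatment and fall inside the window. HIGRT is spread over time. A marker imaged at simulation must have been implanted earlier, and simulation precedes the first fraction. A grade 2+ event from implantation that begins and ends before HIGRT starts therefore belongs to the HIGRT strategy but not to the HIGRT toxicity rate.

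The patients most affected could be missed altogether. Someone harmed during preparation who then receives neither treatment has no treatment date from which a window could run, and Section 4 withdraws that patient.

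What is at stake is the estimated arm difference in acute toxicity, which is a stated secondary objective. The interim grade 4-5 count is also involved, because its wording does not clearly cover preparatory procedures. That rule is triggered when more than 20% of patients have such events, which means more than 8 of the first 40, so single events can matter.

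**Working it through.** **No plan figure to reproduce.** The documents give no assumed rate, precision or power for acute toxicity. The only design figure is for the primary quality-of-life comparison: power 0.82 with 40 per arm, a difference of 5, an SD of 10 and one-sided alpha 0.10. It reproduces (0.83 by the noncentral t) and does not depend on this point.

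**Step 1: is the event counted?**

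| Event | HIGRT starts at first fraction | HIGRT includes simulation and planning (Section 1) |
|---|---|---|
| Fiducial-implantation harm, resolved before HIGRT starts | not counted | not counted |
| Planning-contrast harm, resolved before first fraction | not counted | counted |
| PLA needle, sedation or contrast harm | counted | counted |

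The fiducial gap holds on both readings. The contrast gap holds on only one.

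**Step 2: size of the fiducial omission.** From the documents: 90 patients with equal allocation, so 45 per arm. Assumed, because the documents give nothing: share with fiducials *f* = 0.20 to 0.60; grade 2+ complication per implantation *c* = 0.05 to 0.15; probability of a grade 2+ event inside the window *r* = 0.30, independent of the implantation event.

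The endpoint is per patient, so someone who also has an in-window event is already counted. The understatement is therefore *f* × *c* × (1 − *r*):

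- Low: 0.20 × 0.05 × 0.70 = 0.007, or 0.7 points; × 45 = 0.3 patients.
- High: 0.60 × 0.15 × 0.70 = 0.063, or 6.3 points; × 45 = 2.8 patients.

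**Step 3: set against precision.** The 95% half-width for the arm difference is 1.96 × √(2*p*(1 − *p*)/45).

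- *p* = 0.20: 0.165
- *p* = 0.30: 0.189
- *p* = 0.40: 0.202

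The omission is smaller than this half-width of about 17 to 20 points. It is systematic, however, so the interval does not reflect it.

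**Step 4: the opposing effect.** Section 8.6 gives HIGRT over 2 or 3 weeks. Under the Section 4 definition its window is 90 + 14 = 104 days or 90 + 21 = 111 days, against about 90 for PLA. The ratios are 104/90 = 1.16 and 111/90 = 1.23. As an illustration only, suppose a 30% rate over 90 days and a constant hazard:

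- 104 days: 1 − 0.70^(104/90) = 33.8%, or 3.8 points more.
- 111 days: 1 − 0.70^(111/90) = 35.6%, or 5.6 points more.

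This is of the same order as the omission and in the opposite direction. Under the Section 2.1 wording (90 days from initiation) both arms have 90 days, and the opposing effect disappears while the omission remains.

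**The case against.** The strongest reply is that little is fixed and little is lost. Section 10.3 defines a treatment period, not a toxicity window. The start of HIGRT is undefined, fiducials are optional, and every adverse event is recorded from consent and tabulated continuously by the investigator (Section 18.2).

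Part of this stands. The link from Section 10.3 to the endpoint is an inference, though a natural one, since Sections 2.1 and 4 rely on when treatment starts and Section 10.3 is where the treatment period is defined. Recording is not counting: the prespecified rate still leaves these events out. An undefined start is a reason to settle it before the data are seen.

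A reader might also infer stronger conclusions that the documents do not support:

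- *That the bias always favours HIGRT.* The omission does. The longer HIGRT window under Section 4, and the weekly physician checks during radiotherapy (Section 10.3) with no stated PLA equivalent, push the other way.
- *That planning-contrast harms are certainly excluded.* The Section 1 usage would include them.
- *That the understatement is the simple product of fiducial use and complication rate, 1 to 9 points.* This ignores patients already counted for a later in-window event.
- *That a patient harmed in preparation and never irradiated certainly leaves the comparison.* Section 10.7.2 says otherwise, and such a patient stays evaluable if given MWA. The sections conflict.
- *That the interim rule is biased between arms.* Section 7.1.3 states no arm comparison, and its phrase about timing does not fix the first fraction as the start.

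**Conclusion.** The point holds in a limited form. Under the endpoint as written, a fiducial-implantation harm that resolves before HIGRT starts is not counted on any reading of HIGRT that the documents offer. A planning-contrast harm is left out only if HIGRT starts at the first fraction. PLA's matching harms are counted. The omission lowers the HIGRT rate, while the net effect on the arm difference cannot be signed from the documents.

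Its size cannot be computed from the documents either. The 0.7 to 6.3 points rest wholly on the assumed fiducial use, complication rate, 30% in-window rate and independence. The consequence is confined to a secondary, estimation-only endpoint and, less clearly, to the interim grade 4-5 count. It merits correction because the remedy is cheap and an even harms comparison is one of the trial's stated aims.

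**What to change.** 1. In Secondary Endpoint 4 and Section 7.1.3, keep the treatment-based window and add any event of the relevant grade that is attributed to an arm-specific preparatory procedure after randomisation (for example fiducial implantation or the planning scan), whatever its date relative to the first fraction. Adding only attributed events is better than opening the HIGRT window earlier, which would lengthen that arm's time at risk for unrelated events.
2. Keep every randomised patient who had such a procedure in the toxicity count, even if treatment was not delivered. Reconcile the withdrawal sentence in Section 4 with Sections 10.7.2 and 10.7.3.
3. Use one common window for both arms, reconciling Section 2.1 (90 days from initiation) with Section 4 (through 90 days after treatment), and name the event that starts HIGRT.

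**Cost.** A few sentences. Adverse events are already recorded from consent. The dates of preparatory procedures must be noted, since the dates listed in Section 17 do not name implantation or simulation. The attribution scale in Section 12.1 refers to study therapy and should be extended to these procedures. The HIGRT toxicity rate may look slightly less favourable. Sample size and the primary analysis do not change.

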7.3 Data collection for Quality of Life Surveys (Appendix)

Two surveys will be used to collect baseline, 1 month, 3 month and 6 month QOL information. European Organization for Research and Treatment of Cancer Quality of Life Questionnaire Core-30 (QLQ-C30) will be used to assess general symptom burden, social, financial and psychological burden. The Functional Assessment of Cancer Therapy-Hepatobiliary (FACT-Hep) survey will be used to assess liver specific symptom burden. Both surveys will be collected at baseline (prior to initiation of any therapy) and at 1, 3 and 6 month time marks. Good faith effort will be made to collect survey data in person and on paper if at all possible. If in person or on paper survey collection is not possible, oral survey data collect is allowed by authorized study staff either in person or on the phone. Good faith effort to collect data will allow that surveys may be mailed to subjects. Alternatively surveys may be completed via a secure link electronically. Surveys will be collected within a 2 week period of the planned time mark.

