8.8 Treatment Delivery

Ideally treatment will be delivered on consecutive days, for both the 5 and 10 fraction regimens. It is recommended that all treatment be completed in 2 weeks (for 5 fraction regimen) and 3 weeks (for 10 fraction regimen).

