9.4 Post-PLA monitoring

Immediately following the intervention, the patient will be monitored in a recovery area with a dedicated nursing staff; any early procedure-related adverse event will be documented. After appropriate post-procedure monitoring, the patient is discharged to home if all necessary criteria for discharge are met.

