11.1 Medical History

Prior to enrollment, all patients will have a complete medical History and Physical. Medical history will be documented in standard format including a history and physical exam by Gastroenterology, Medical Oncology or Radiation Oncology. Weekly treatment checks during radiation therapy will be focused histories.

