12. SAFETY MONITORING AND REPORTING

The PI or treating MD is responsible for the identification and documentation of adverse events and serious adverse events, as defined below. At each study visit, the PI or designee must assess, through non-suggestive inquiries of the subject or evaluation of study assessments, whether an AE or SAE has occurred.

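### Physician checks are scheduled weekly during HIGRT but not at all between PLA discharge and month 1, so the planned arm difference in acute grade 2+ toxicity is at risk of unequal detection

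*Combined protocol and SAP*

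**What the plan says.** **HIGRT.** Section 10.3 states: "They will also undergo weekly assessment by radiation oncologist during radiotherapy". Section 11.1 describes the content: "Weekly treatment checks during radiation therapy will be focused histories". On course length, section 8.8 says: "It is recommended that all treatment be completed in 2 weeks (for 5 fraction regimen) and 3 weeks (for 10 fraction regimen". The same section prefers delivery on consecutive days.

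**PLA.** This is a single outpatient procedure. Early procedure-related events are documented in the recovery area (9.4), and a follow-up CT looks for acute complications (9.2). Then: "After appropriate post-procedure monitoring, the patient is discharged to home if all necessary criteria for discharge are met". No written section schedules a further contact before month 1. Among the anticipated PLA risks, section 7.1.3 lists "pain (muscle aches or spasm may occur for 3-5 days", together with nausea/vomiting and fever.

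**Both arms after treatment.** Section 10.3 places assessments at months 1, 3 and 6 for the quality-of-life surveys, and section 11.2 counts these from completion of treatment. Section 7.3 prefers collection in person but allows phone and electronic completion, and adds: "Good faith effort to collect data will allow that surveys may be mailed to subjects". Restaging imaging and labs follow standard of care, typically at 1 and 3 months, with deviations left to the treating physician. The one visit for which section 10 names toxicity assessment is month 6 (10.4; 180 days, plus or minus 30).

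**Adverse-event rules.** Section 12 says: "At each study visit, the PI or designee must assess" whether an event has occurred. Section 12.1 requires all events from consent to the End of Study visit to be recorded.

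**Endpoint.** Secondary Endpoint 4 in section 4 counts any grade 2+ event from treatment through 90 days afterwards, and states: "The arm difference in acute toxicity rate will be estimated with its 95% CI".

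**The concern.** A between-arm difference in the proportion of patients with an event is interpretable only if events have a similar chance of being found in each arm. Here a symptom arising during the HIGRT course meets a scheduled physician contact within about a week. A symptom arising after PLA discharge meets none until month 1, by which time several days of pain, nausea or fever may have resolved. If the month 1 survey comes back by mail or electronic link, there may be no clinical conversation at that point either.

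At stake is the direction of a reported comparison. Poorer detection after PLA would lower the recorded PLA rate and move the difference against HIGRT. The confidence interval would not show it, because the interval reflects sampling error only. Brief grade 2 events are the exposed class. Severe events, or those leading to hospital admission, are much less likely to be lost.

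**Working it through.** **1. The plan's own figures.** The plan gives no expected rate, precision target or power for acute toxicity, so there is no figure to reproduce for this endpoint. The only power figure concerns the primary endpoint: 40 per arm, difference 5, SD of change 10, one-sided alpha 0.10. The standardised difference is 5 / (10 × √(2/40)) = 2.236, and Φ(2.236 − 1.282) = 0.83 (0.827 with the noncentral t), against 0.82 stated. It reproduces, and nothing here touches it.

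**2. Scheduled opportunities to detect an event, side by side.**

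| Period | HIGRT | PLA |
|---|---|---|
| Treatment | Weekly check: about 2–3 over a 2- or 3-week course; 1–2 if fractions run on consecutive days (5 fractions in one week, 10 in two) | Recovery-area documentation and CT, same day |
| End of treatment to month 1 | None | None |
| Months 1 and 3 | Survey contact, possibly remote; standard-of-care imaging and labs | Same |
| Month 6 | Toxicity assessment named | Same |

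The arms differ only in the first row. The second row is empty for both, but what falls into it differs. HIGRT events during the treatment weeks precede the gap. PLA aches lasting 3–5 days would run largely inside it, because the patient has gone home.

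**3. Whether month 1 closes the gap.** The section 12 enquiry is tied to study visits, and a mailed or electronic survey is not evidently a visit. The surveys are quality-of-life instruments, not CTCAE reviews. Standard-of-care follow-up is described as imaging and labs, which would not reliably bring out a symptom that has resolved. Section 10 itself names toxicity only at month 6, about 90 days after the acute window closes.

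**4. Size, under assumptions.** The documents give no toxicity rate and no detection probability. With equal true rates:

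spurious difference = true rate × (HIGRT detection − PLA detection)

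Assume HIGRT detection of 100% and PLA detection of 90%, 80%, 70% or 60%:

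- true rate 20%: 2, 4, 6, 8 points
- true rate 30%: 3, 6, 9, 12 points
- true rate 50%: 5, 10, 15, 20 points

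If detection is 90% in HIGRT and 70% in PLA at a true rate of 30%, the difference is 0.30 × 0.20 = 6 points. If detection is equal, it is zero.

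For scale, take 45 per arm with recorded rates of 30% and 24%. The 95% half-width is 1.96 × √(0.30×0.70/45 + 0.24×0.76/45) = 0.183, about 18 points. Over the 100%-detection cases above it runs from about 15 to 21 points.

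**5. Recall, if a common enquiry is added at month 1.** Month 1 is counted from completion of treatment. Back to treatment start, a PLA patient recalls about 4 weeks and a HIGRT patient 2 + 4 to 3 + 4, that is 6–7 weeks.

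**The case against.** The case against has several sound parts.

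- **Under-counting is not shown.** A reader might infer that PLA events will be under-counted. The documents do not establish that. Same-day documentation and CT cover the immediate period, section 12.1 requires all events to be recorded, and the section 12 enquiry asks whether an event has occurred, so earlier events are in scope. This stands. However, a duty to record depends on detection, and the scheduled opportunities for detection differ.
- **A count of 2–3 checks against 0 is not like for like.** It starts HIGRT at the first fraction and PLA after the procedure. From the end of treatment to month 1 both arms have none, so HIGRT events after the last fraction can be missed too. This stands.
- **The weekly checks are only focused histories.** Nothing calls them study visits or CTCAE reviews, so full HIGRT detection is an assumption. This also stands and limits the likely size.
- **Remote surveys are allowed in both arms.** They are therefore not an asymmetry. They matter only because month 1 cannot be relied on to recover what was missed.
- **The share of brief grade 2 events is unknown.** A reader might suppose that they make up most of this endpoint. Section 7.1.3 gives a duration for pain but no grade, and no rates are given, so that cannot be claimed.
- **The endpoint is secondary and estimated without a test.** In nearly all the illustrated cases the bias is smaller than the sampling half-width. This is correct and keeps the point in proportion, but averaging over patients does not remove a bias.

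What remains is the on-treatment asymmetry and the lack of a named toxicity enquiry within the acute window.

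**Conclusion.** The concern holds as a risk of differential detection, probably in the direction that makes HIGRT look relatively worse on acute grade 2+ toxicity. It rests on two features of the text: scheduled checks over the treatment weeks in one arm only, and no section 10 contact within the 90-day window at which toxicity assessment is named. The size cannot be computed from the documents. The 3–12 points at a 30% true rate depend entirely on the assumed detection probabilities and would be zero if detection were equal.

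The primary quality-of-life analysis is unaffected. The interim safety review uses grade 4–5 events, which are unlikely to be missed. If the section 5 schema shows an early post-PLA contact that the written sections do not mention, the gap is correspondingly smaller.

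A reader might conclude that the comparison should be restricted to events elicited at contacts common to both arms. The endpoint definition does not support that. Restriction would discard known grade 2+ events during HIGRT and rest the result on unequal recall, 6–7 weeks against about 4. It belongs in a sensitivity analysis. The change is worth making because it is cheap and improves a comparison the plan intends to report.

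**What to change.** 1. In sections 10.3 and 12, require the same structured CTCAE enquiry in both arms at months 1 and 3. It should cover the whole period since treatment start, and be done by phone when the survey is mailed or electronic.
2. Keep the all-source grade 2+ rate in section 4 as the endpoint.
3. Add a sensitivity estimate of the arm difference, with its 95% CI, that leaves out events found only at weekly HIGRT checks. This needs a field on the adverse-event form for where each event was first detected. Read it beside the main estimate: it drops genuine HIGRT events and so can err the other way.
4. State the remaining on-treatment asymmetry as a limitation of the comparison.

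The cost is a short checklist at contacts that already occur, some phone calls, one form field and one added analysis. Recall error remains, and is longer in HIGRT at month 1. Sample size and treatment are unchanged. The enquiry should be introduced prospectively, since brief events not elicited by month 1 are hard to recover later. If it is not adopted, the limitation statement is the minimum.
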